6.1 Study Intervention(s) Administered

The study medications to be used in this study are outlined in Table 1.

First Randomization at Visit 3/Day 1/Randomization:

All qualified participants will be randomized to receive 2 tablets per day of either:

- Ertugliflozin 5 mg and placebo matching ertugliflozin 15 mg –OR-
- Placebo matching ertugliflozin 5 mg and placebo matching ertugliflozin 15 mg

Second Randomization at Visit 5/Week 12:

Eligible participants in the ertugliflozin 5 mg group

- Treated with ertugliflozin 5 mg: FS A1C ≥7.0% (53 mmol/mol)
- Treated with ertugliflozin 5 mg and insulin: FS A1C ≥7.0% (53 mmol/mol) and FFSG ≥110 mg/dL (6.1 mmol/L)

will have a second randomization to receive 2 tablets per day of either:

- Ertugliflozin 5 mg and placebo matching ertugliflozin 15 mg OR-
- Ertugliflozin 15 mg and placebo matching ertugliflozin 5 mg.

Eligible participants in the placebo group

- Treated with placebo alone: FS A1C \geq 7.0% (53 mmol/mol)
- Treated with placebo and insulin: FS A1C ≥7.0% (53 mmol/mol) and a FFSG ≥110 mg/dL (6.1 mmol/L)

will undergo a mock second randomization to maintain blinding, with no change in study medication. Participants who do not meet the threshold(s) for a second randomization will continue on ertugliflozin 5 mg/placebo.

If a participant discontinues study medication before Visit 5/Week 12, the second randomization should not be performed.

Table 1 Study Medications

Arm Name	Arm Type	Medication Name	Туре	Dose Formu- lation	Unit Dose Strength(s)	Dosage Level(s)	Route of Adminis- tration	Regimen/ Treatment Period	Use	IMP or NIMP/ AxMP	Sourcing
Placebo Run-in	Other	Placebo matching ertugliflozin 5 mg	Other	Tablet	0 mg	1 Tablet qd	Oral	Visit 2 to Visit 3 (Placebo Run-in Period)	Placebo	IMP	Provided centrally by Sponsor
Placebo Run-in	Other	Placebo matching ertugliflozin 15 mg	Other	Tablet	0 mg	1 Tablet qd	Oral	Visit 2 to Visit 3 (Placebo Run-in Period)	Placebo	IMP	Provided centrally by Sponsor
Ertugliflozin 5 mg	Experimental	Ertugliflozin 5 mg	Drug	Tablet	5 mg	1 Tablet qd	Oral	Visit 3 to Visit 5/8 (Double- blind Treatment Period)	Test Product	IMP	Provided centrally by Sponsor
Ertugliflozin 5 mg	Experimental	Placebo matching ertugliflozin 15 mg	Other	Tablet	0 mg	1 Tablet qd	Oral	Visit 3 to Visit 5/8 (Double- blind Treatment Period)	Placebo	IMP	Provided centrally by Sponsor

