6.3 Measures to Minimize Bias: Randomization and Blinding

6.3.1 Intervention Assignment

Intervention allocation/randomization will occur centrally using an interactive response technology (IRT) system. At **Visit 3/Day 1/Randomization**, there will be 2 study intervention arms. Participants will be assigned randomly in a 2:1 ratio to ertugliflozin 5 mg or placebo.

At **Visit 5/Week 12**, all eligible participants (Section 6.1) will undergo a second randomization. Eligible participants in the ertugliflozin 5 mg group will be randomized in a 1:1 ratio to either stay on ertugliflozin 5 mg or up-titrate to ertugliflozin 15 mg (Section 8.1.14). Eligible participants in the placebo group will participate in the second randomization, but all will remain on placebo and be mock-titrated to preserve blinding.

If the PK IA (Section 9.7) results in a decision to drop the 15 mg dose, then:

- 1. The second randomization at **Visit 5/Week 12** will be discontinued and the corresponding FS A1C and FFSG should not be performed (the central laboratory A1C will still be performed).
- 2. Ongoing participants who have reached **Visit 5/Week 12** or beyond on study medication will return to the site to have blinded study medication redispensed through IRT to maintain blinding. Participants receiving placebo or ertugliflozin 5 mg will continue to receive the same medication. Participants who are receiving ertugliflozin 15 mg will be down-titrated to the ertugliflozin 5 mg dose for the remainder of the study.

If the ertugliflozin 15 mg dose is continued, the second randomization at **Visit 5/Week 12** will be monitored by the unblinded DMC statistician so that ~30 participants are up-titrated to ertugliflozin 15 mg/day.

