8.1.14 Second Randomization

At **Visit 5/Week 12**, all participants will have an FS A1C measured at the site (Section 8.3.8.1). Participants will undergo a second randomization as outlined in the SoA *if* their FS A1C is \geq 7.0% (53 mmol/mol). At this second randomization, eligible participants on ertugliflozin 5 mg will be assigned to continue on the 5 mg dose or up-titrate to the ertugliflozin 15 mg dose in a 1:1 ratio. Eligible participants in the placebo group will participate in the second randomization, but all will remain on placebo and be mock-titrated to preserve blinding. Note: The up-titration criteria for participants on insulin will include a FFSG \geq 110 mg/dL (6.1 mmol/L) in addition to A1C \geq 7.0% (53 mmol/mol) at **Visit 5/Week 12**. Participants who do not meet the threshold(s) for a second randomization will continue on ertugliflozin 5 mg/placebo. If a participant discontinues study medication before **Visit 5/Week 12**, the second randomization (and related assessments) should not be performed.

At **Visit 5/Week 12**, a second allocation number will be randomly assigned by the IRT system for participants on ertugliflozin 5 mg who meet up-titration criteria. During the study, only the unblinded statistician will have access to this allocation number and its associated treatment assignment. Participants who undergo the second randomization will retain their initial randomization number assigned at **Visit 3/Day 1/Randomization** to uniquely identify them by blinded personnel during the study.

The unblinded statistician who supports the DMC described in Section 9.7 will review the number of participants randomized to the ertugliflozin 5 mg and ertugliflozin 15 mg group at the **Visit 5/Week 12** second randomization and throughout the study. Based on the distribution of participants within the ertugliflozin 5 mg and 15 mg arms, the randomization ratio for the second randomization at **Visit 5/Week 12** may be adjusted in order to achieve approximately 30 participants in the ertugliflozin 15 mg arm.

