9.4.2 Safety Endpoints

The descriptions of the safety measurements and timepoints at which they are measured are described in Section 8.3 and Section 1.3. The safety endpoints to be analyzed are listed in Table 9. Safety analyses will be conducted across Week 0 to Week 54 (Phase A+B) with selected analyses also done across Week 0 to Week 24 (Phase A).

Events of symptomatic hypoglycemia, AEs associated with genital mycotic infection (gender specific), hypovolemia, and UTI are considered Tier 1 events.

Hypoglycemia will be described using the following definitions:

- Symptomatic hypoglycemia: Episodes with clinical symptoms reported by the investigator as hypoglycemia (biochemical documentation not required).
- Severe hypoglycemia: Episodes that required assistance, either medical or non-medical. Episodes with a markedly depressed level of consciousness, a loss of consciousness, or seizure will be classified as having required medical assistance, whether or not medical assistance was obtained.
- Documented symptomatic hypoglycemia: Episodes with clinical symptoms attributed to hypoglycemia with a glucose level ≤70 mg/dL (3.9 mmol/L) or <54 mg/dL (3.0 mmol/L).
- Asymptomatic hypoglycemia: Episodes without symptoms attributed to hypoglycemia, but with a documented glucose level ≤70 mg/dL (3.9 mmol/L) or <54 mg/dL (3.0 mmol/L).
- Documented hypoglycemia (symptomatic and asymptomatic): Episodes with a glucose level ≤70 mg/dL (3.9 mmol/L) or <54 mg/dL (3.0 mmol/L), with or without symptoms.

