9.6 Statistical Methods

Statistical testing and inference for safety analyses are described in Section 9.6.2. Efficacy results that will be deemed to be statistically significant after consideration of the Type I error control strategy are described in Section 9.8. Nominal p-values (ie, unadjusted for multiplicity) may be computed for other efficacy analyses for descriptive purposes rather than for assessing statistical significance.

The primary approach for all efficacy and safety analyses will pool participants from both ertugliflozin dose groups (5 mg and 15 mg) for comparison with placebo. In addition, A1C change from Baseline at Week 24 will be compared for 2 treatment strategies, (1) dose-optimized ertugliflozin versus placebo and (2) ertugliflozin 5 mg versus placebo. Dose-optimized ertugliflozin consists of participants who were randomized to ertugliflozin and either did not meet the re-randomization criterion at Week 12 or who met the re-randomization criterion and were re-randomized to ertugliflozin 15 mg. Descriptive statistics will be used for efficacy and safety endpoints to summarize ertugliflozin data by dose group and by combined doses. Descriptive statistics will also be used to summarize the individual ertugliflozin dose arms in the subset of participants who were re-randomized at Visit 5/Week 12.

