9.6.2 Statistical Methods for Safety Analyses

Safety and tolerability will be assessed by clinical review of all relevant parameters including AEs, laboratory tests, and vital signs measurements. Safety analyses will be conducted across Week 0 to Week 54 (Phase A+B) with selected analyses also done across Week 0 to

[†] The primary analysis for the TP estimand will use RD to impute missing data if RD is feasible. If RD is not feasible, WI will be used.

Week 24 (Phase A). For safety and tolerability analyses, the pooled ertugliflozin group (5 mg and 15 mg) will be compared with the placebo group.

Participants will be included in the treatment group corresponding to the study treatment they actually received for the analysis of safety data using the APaT population. This will be the treatment group to which they are randomized, except for any participants who take incorrect study treatment for the entire treatment period. Such participants will be included in the treatment group corresponding to the study treatment actually received.

The following analysis approaches will be used:

All safety endpoints except hypoglycemia will be summarized regardless of the initiation of rescue or intensification therapy. This approach is referred to as the "including rescue" approach (IR). The Treatment Period will include all data from randomization up to 14 days after the last dose of study treatment for AEs, Tanner Staging and abdominal ultrasounds, up to 2 days after the last dose of study treatment for laboratory endpoints, and up to 5 days after the last dose for growth velocity and vital signs with the exception of analyses of Phase A alone, for which the additional follow-up days will not be included for participants who continue into Phase B (ie, Phase B data will be excluded from analyses of Phase A only).

SAEs and deaths will also be summarized inclusive of all post-randomization follow-up (APRFU), regardless of study treatment adherence and without an upper day limit.

AE summary measures will be tabulated by ertugliflozin dose in the subset of participants who were re-randomized at Visit 5/Week 12.

Hypoglycemia endpoints will be summarized excluding data collected following the initiation of rescue therapy or intensification therapy. This approach is referred to as the "excluding rescue" approach (ER).

Table 8 summarizes the analysis strategy by study phase and analysis approach.

Phase	Analysis Approach	Endpoints

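### As defined, the by-dose adverse event table includes the 12 weeks both groups spent on 5 mg, and the wider by-dose-group summary puts every early stop in the 5 mg column

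*Combined protocol and SAP*

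**What the plan says.** Section 9.6.2 gives one AE window: "The Treatment Period will include all data from randomization up to 14 days after the last dose of study treatment for AEs". Table 8 lists Phase A, Phase A+B, and Phase A+B with all post-randomization follow-up. Sections 9.4.2 and 9.6.2 count these from Week 0. No window starts at the second randomization.

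Two by-dose safety outputs are planned.

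- Section 9.6.2: "AE summary measures will be tabulated by ertugliflozin dose in the subset of participants who were re-randomized at Visit 5/Week 12". The AE summary measures defined there are proportions of participants with at least one event of a given kind.
- Section 9.6: "Descriptive statistics will be used for efficacy and safety endpoints to summarize ertugliflozin data by dose group and by combined doses". The next sentence adds a descriptive summary of the dose arms within the re-randomized subset, so the first summary is evidently wider than that subset. The term dose group is not defined.

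Everyone randomized to ertugliflozin starts on 5 mg. Section 6.3.1 describes the Week 12 step, at which 15 mg first becomes available: "Eligible participants in the ertugliflozin 5 mg group will be randomized in a 1:1 ratio to either stay on ertugliflozin 5 mg or up-titrate". Section 6.1 adds: "If a participant discontinues study medication before Visit 5/Week 12, the second randomization should not be performed". Section 8.1.14 says the ratio "may be adjusted in order to achieve approximately 30 participants in the ertugliflozin 15 mg arm".

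The main safety comparison is pooled: "For safety and tolerability analyses, the pooled ertugliflozin group (5 mg and 15 mg) will be compared with the placebo group". The Section 9.6.2 rule for assigning participants to treatment groups makes an exception only for those on the wrong treatment throughout. It does not say where to count an AE on 5 mg in someone who later moves to 15 mg.

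**The concern.** The safety analysis pools the two doses because adult data showed similar profiles (Section 4.3). The by-dose tables are the plan's own pediatric look at that premise, and each has a feature that could mislead.

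In the re-randomized table, a participant with an AE in Week 5 is already counted when the doses diverge at Week 12 and can add nothing to the contrast afterwards. That masks part of any difference between doses.

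In the by-dose-group summary, a participant must still be on study medication at Week 12 to enter the 15 mg group. Nobody in that group can have stopped for an AE before then. If the 5 mg group is everyone else, it holds all the early stops. Discontinuation due to an AE is a primary safety endpoint (Section 3), so a built-in advantage for the higher dose would be easy to misread.

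**Working it through.** The plan states no figure for the by-dose tables, so there is nothing to reproduce.

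**Inputs from the documents.** 110 participants on ertugliflozin (Section 9.9); about 30 on 15 mg (Section 8.1.14); second randomization at Week 12; windows to Week 24 and Week 54.

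**Assumptions, not in the documents.** p12 from 1% to 60%; a hazard ratio of 2 for 15 mg versus 5 mg after Week 12, with constant hazards otherwise; AE discontinuation over 54 weeks of 4%, 8% or 15%.

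**1. Share of the 15 mg column's planned window spent on 5 mg.** Phase A: 12/24 = 50%. Phase A+B: 12/54 = 22%.

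**2. Effect on the re-randomized table.** Both columns share p12 in expectation. For either dose,

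P(event, Day 1 count) = p12 + (1 - p12) × P(event after Week 12, given none before).

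Subtracting the columns, p12 cancels:

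RD(Day 1 count) = (1 - p12) × RD(Week 12 count).

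The factor is exact if an early event says nothing about a later one, as under constant hazards; otherwise it is approximate.

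Worked case, p12 = 20%, hazard ratio 2, to Week 24:

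- Week 12 count: 5 mg 20.0%; 15 mg 1 - 0.8² = 36.0%; RD 16.0 points; RR 1.80.
- Day 1 count: 5 mg 1 - 0.8² = 36.0%; 15 mg 1 - 0.8³ = 48.8%; RD 12.8 points; RR 1.36.
- Check: 0.80 × 16.0 = 12.8.

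Range, hazard ratio 2, to Week 24:

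| p12 | RD, Week 12 count | RD, Day 1 count | Factor |
|---|---|---|---|
| 1% | 1.0 | 1.0 | 0.99 |
| 20% | 16.0 | 12.8 | 0.80 |
| 40% | 24.0 | 14.4 | 0.60 |
| 60% | 24.0 | 9.6 | 0.40 |

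For rare events (p12 = 1%) the risk difference hardly moves, but the risk ratio falls from 1.99 to 1.49 at Week 24 and from 1.97 to 1.75 at Week 54.

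**3. Survivor bias in the re-randomized table.** Anyone who stops before Week 12 is not re-randomized, so both columns contain only people still on 5 mg at Week 12, split at random. A 4,000-run simulation with no dose effect, an 8% baseline rate and varying individual risk gave AE discontinuation of 5.8% (15 mg) and 5.7% (5 mg), with a simulation standard error of about 0.07 points on the 15 mg figure. The columns are equal within simulation error. Neither can contain an AE discontinuation before Week 12, so that measure is not diluted.

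**4. The by-dose-group summary, if 5 mg means never up-titrated.** That gives 30 on 15 mg and 80 on 5 mg. With a constant hazard and no dose effect, take an 8% 54-week rate: the probability of stopping is 1.84% over Weeks 0-12 and 6.28% over Weeks 12-54. Early stops: 110 × 0.0184 = 2.02, all in the 5 mg group. Later stops there: (80 - 2.02) × 0.0628 = 4.90. The 5 mg rate is 6.92/80 = 8.65%, against 6.28% on 15 mg.

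| Assumed 54-week rate | Early stops | 15 mg | 5 mg (all others) |
|---|---|---|---|
| 4% | 0.99 | 3.13% | 4.33% |
| 8% | 2.02 | 6.28% | 8.65% |
| 15% | 3.90 | 11.87% | 16.17% |

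**5. Precision.** With 30 per arm in the worked case, the standard error of the risk difference is √(0.20×0.80/30 + 0.36×0.64/30) = 11.4 points for the Week 12 count and √(0.36×0.64/30 + 0.488×0.512/30) = 12.7 points for the Day 1 count. Power for a two-sided 5% test would be about 28% and 17%.

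**The case against.** The strongest reply is that little depends on these tables. They are descriptive, no 15 mg versus 5 mg test is planned, and about 30 participants receive 15 mg. Step 5 shows that neither count gives a precise dose comparison. This stands, and it limits the weight of the point.

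The plan also never says that the re-randomized table starts at Day 1. It says randomization, and the trial has two. A supplemental SAP, which is not available here, may settle it. That is fair, but the surrounding text runs safety from Week 0 and offers no other window, so Day 1 is the default a programmer would apply.

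For Section 9.6, dose group is undefined, and the randomized summary is promised beside the wider one. The imbalance in step 4 therefore depends on a reading, though a natural one.

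A reader might go further than the documents allow in three ways.

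- That the re-randomized table suffers from survivor bias. It does not, because early stoppers are in neither column.
- That early events are loaded onto 15 mg. They enter both columns equally in expectation.
- That the attenuation has a known size. Any single percentage merely restates an assumed p12.

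**Conclusion.** The point holds as a cheap improvement. Under the plan's only AE window, the re-randomized table mixes 12 weeks of common 5 mg treatment into both columns, and the risk difference is multiplied by (1 - p12). The 50% and 22% exposure shares need no assumption beyond the planned schedule. The size of the dilution depends on p12, for which the documents give no value. The table stays a fair randomized contrast apart from this dilution, and AE discontinuation in it is untouched. If the 1:1 ratio is changed mid-study, the two doses would no longer be balanced over calendar time.

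The by-dose-group summary has a different problem, conditional on 5 mg meaning never up-titrated: it favors 15 mg on early discontinuation by construction, by 1.2 to 4.3 points over the assumed rates (4.33 - 3.13 and 16.17 - 11.87).

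A reader might infer that the primary safety conclusions are compromised. The documents do not support that, because the planned comparison pools the doses against placebo and neither issue affects it.

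**What to change.** In Section 9.6.2, state that by-dose AE tables in the re-randomized subset count only events with onset on or after the first dose dispensed at Visit 5/Week 12.

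In Section 9.6, either limit by-dose AE summaries to that subset, or assign each AE to the dose being taken at onset and use person-time denominators.

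Leave laboratory and vital-sign baselines as they are unless Week 12 values are collected. Table 14 maps no safety laboratory results to Week 12, and the detailed rows of the Schedule of Activities are redacted, so a Visit 5 baseline cannot be assumed to exist.

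The cost is a few sentences and a table shell. The downside is fewer events in the by-dose tables. The pooled tables do not change.

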4 STUDY DESIGN

4.1 Overall Design

This is a randomized, placebo-controlled, parallel-group, multi-site, double-blind study of ertugliflozin in pediatric participants (10 to 17 years of age, inclusive) with T2DM, including a randomly assigned up-titration of eligible participants after a second randomization at **Visit 5/Week 12** (Section 8.1.14). Participants will take part in the study for approximately 58 weeks, including an approximately 1-week screening period (**Visit 1/Screening** to **Visit 2/Week -1**), an approximately 1-week single-blind placebo run-in period (**Visit 2/Week -1** to **Visit 3/Day 1/Randomization**), an approximately 54-week double-blind treatment period (including a 24-week Phase A + 30-week Phase B), and a telephone contact 14 days after the last dose of study medication. All participants will continue to receive metformin ± insulin background therapy during the course of the study. The primary efficacy endpoint for the study will be evaluated using data from Phase A. The 30-week Phase B will provide a longer-term evaluation of ertugliflozin safety and efficacy in this pediatric population.

The mitigation strategies for managing participants with poor glycemic control differ between the Phase A and Phase B periods (Section 6.5.1). During the 24-week Phase A period, participants meeting progressively lower FPG thresholds (Table 3) will be rescued. In Phase B, therapy for participants meeting even lower glycemic thresholds will be intensified (Table 4) to prevent prolonged exposure to hyperglycemia.

At **Visit 3/Day 1/Randomization**, eligible participants will be randomized in a 2:1 ratio to ertugliflozin 5 mg or placebo. At **Visit 5/Week 12**, eligible participants in the ertugliflozin 5 mg treatment group (Section 6.1) will undergo a second randomization in a 1:1 ratio to either continue on ertugliflozin 5 mg or up-titrate to ertugliflozin 15 mg. Similarly, eligible participants in the placebo group will be mock-titrated (Section 6.1) to maintain the blind. Participants who do not meet the threshold(s) for a second randomization will continue on

ertugliflozin 5 mg/placebo. Additional details are provided in Section 9. If a participant discontinues study medication before **Visit 5/Week 12**, the second randomization should not be performed.

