Starting from **Visit 6/Week 24**, FFSG and FS A1C will be measured at scheduled and unscheduled site visits, and glycemic intensification will be initiated if the participant meets criteria (Table 4). Between site visits, participants with FFSG >130 mg/dL (7.2 mmol/L) at home for 3 consecutive days will come to the site for an **Unscheduled Visit** if, in the investigator's judgment, the participant has been compliant with study medication and diet/exercise recommendations. At the unscheduled site visit, the participant's FFSG and FS A1C will be measured, and the participant will initiate glycemic intensification if both values meet criteria (Table 4). If the participant is on metformin alone, insulin glargine will be initiated (dose at the investigator's discretion based on accepted local, national or international guidelines). If the participant is on metformin + insulin the total daily insulin dose will be increased by ≥15% (Table 2).

 Participant's Background Therapy
 Phase A Rescue Therapy OR Phase B Intensification Therapy (for participants not rescued in Phase A)

 Metformin alone Metformin + Insulin
 Insulin glargine Increase insulin dose ≥15%

Table 2 Glycemic Rescue/Intensification Strategy

Note: In Phase A and Phase B, participants requiring transient (ie, <14 days) initiation of insulin or an increase in insulin (≥15% of the dose at baseline), for participants on background insulin therapy (eg, an intercurrent illness) will not be considered as having initiated rescue/intensification. Down-titration or weaning of insulin after a temporary initiation or increase in dose should occur at the investigator's discretion.

Note that participants rescued or intensified with basal insulin for 6 weeks or more, can have prandial insulin added at the investigator's discretion. The choice, dose, and titration of prandial insulin will be the investigator's responsibility.

Participants <18 years of age, who refuse to initiate insulin or up-titrate their background insulin (or for whom it is considered inappropriate) when glycemic thresholds for rescue/intensification are met will be discontinued from study medication (see Section 7.1). Participants ≥18 years of age can be rescued or undergo glycemic intensification using any of the antihyperglycemic agents approved for use with ertugliflozin.

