9.5.2 Safety Analysis Populations

Safety analyses will be performed in the APaT population consisting of all randomized participants who received at least one dose of study treatment and will include participants in the ertugliflozin 15 mg dose group, regardless of the outcome of the PK IA.

At least 1 laboratory or vital sign measurement obtained subsequent to at least one dose of study treatment is required for inclusion in the analysis of each specific parameter. To assess change from baseline, a baseline measurement is also required.

Safety analysis will be based on observed data only. No imputation will be performed for missing data.

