Phase A	Treatment period, IR	all AE endpoints and PDLCs
Thase A	Treatment period, ER	hypoglycemia endpoints
A + B	Treatment period, IR	all safety endpoints except for hypoglycemia endpoints
	Treatment period, ER	hypoglycemia endpoints
	Treatment period + APRFU, IR	SAEs and deaths

Table 8 Analysis Strategy for Safety Endpoints by Study Phase

AE = adverse event; APRFU = all post-randomization follow-up; ER = excluding data after initiation of glycemic rescue/intensification therapy; IR = including data after initiation of glycemic rescue/intensification therapy; PDLC = predefined limits of change; SAE = serious adverse event(s).

The analysis of safety results will follow a tiered approach (Table 9). The tiers differ with respect to the analyses that will be performed. Adverse events (specific terms as well as system organ class terms) are either prespecified as "Tier 1" endpoints or will be classified as belonging to "Tier 2" or "Tier 3" based on the number of events observed.

Tier 1 Events

Safety parameters or AEs of special interest that are identified a priori constitute "Tier 1" safety endpoints that will be tested for statistical significance with p-values and 95% CIs to be provided for between-treatment differences in the proportion of participants with events; these analyses will be performed using the M&N method [Miettinen, O. and Nurminen, M. 1985], an unconditional, asymptotic method. For this protocol, events of symptomatic hypoglycemia, and AEs associated with genital mycotic infection (gender specific), hypovolemia, and UTI are considered Tier 1 events. AEs associated with UTI, hypovolemia, and genital mycotic infection will be identified by Custom MedDRA queries (CMQ), which will be defined in the sSAP.

Tier 2 Events

Tier 2 parameters will be assessed via point estimates with 95% CIs provided for differences in the proportion of participants with events (also via the M&N method [Miettinen, O. and Nurminen, M. 1985]).

Membership in Tier 2 requires that at least 8 participants in the combined ertugliflozin group or 2 participants in the placebo group exhibit the event; all other adverse events and predefined limits of change will belong to Tier 3.

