95% CI for **Treatment Descriptive** Tier Safety Variable/Endpoint p-Value **Comparisons Statistics** Tier 1 AEs of genital mycotic infection (gender X X X specific) AEs of hypovolemia X X X X X X Events of symptomatic hypoglycemia X X AEs of UTI X Tier 2[†] Episodes of severe hypoglycemia X X X X Requiring medical assistance X X X X Not requiring medical assistance X Episodes of documented hypoglycemia X X AE summary measures X X X Specific AEs ‡ or PDLCs (incidence ≥ 8 participants in the combined ertugliflozin group or ≥ 2 participants in the placebo group) X Tier 3 Specific AEs[‡] or PDLCs (incidence <8 participants in combined ertugliflozin group or <2 participants in the placebo group) Additional hypoglycemia endpoints X Change from baseline results (labs [including X bone biomarkers], vital signs, and abdominal ultrasounds) X Growth velocity and Tanner Staging

Table 9 Analysis Strategy for Safety

AE = adverse event; CI = confidence interval; PDLC = predefined limits of change; UTI = urinary tract infection; X = results will be provided.

Analysis of Hypoglycemia

For the hypoglycemia endpoints described in Section 9.4.2, the analyses of hypoglycemia will be performed separately for participants on a background of insulin and for participants not on a background of insulin at screening. Analyses of hypoglycemia combining participants on and not on a background of insulin are not planned.

[†] Endpoints listed here will qualify for Tier 2 only if the incidence is ≥8 participants in the combined ertugliflozin group or ≥2 participants in the placebo group.

[‡] Includes only those endpoints not prespecified as Tier 1 or not already prespecified as Tier 2 endpoints.

Tier 1 endpoints for hypoglycemia are the percentages of participants experiencing 1 or more episodes of symptomatic hypoglycemia.

Tier 2 endpoints for hypoglycemia are the percentages of participants experiencing 1 or more episodes of documented or severe hypoglycemia defined above. Summaries will be provided for all episodes.

Tier 3 endpoints for hypoglycemia are the percentages of participants with documented hypoglycemia as defined above:

- by lowest reported glucose category (<54 mg/dL [3.0 mmol/L], ≤70 mg/dL [3.9 mmol/L]); and
- by number of episodes.

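### Phase A+B hypoglycemia is compared as a crude percentage although counting stops at rescue or intensification; if ertugliflozin works as planned, the comparison is expected to be biased against it, by about 5–20% relative under assumed rates

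*Combined protocol and SAP*

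**What the plan says.** Four rules in the safety plan act together.

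- **Data counted.** Section 9.6.2 states: "Hypoglycemia endpoints will be summarized excluding data collected following the initiation of rescue therapy or intensification therapy". Table 8 assigns hypoglycemia to "Treatment period, ER" in Phase A and again in Phase A+B. All other safety endpoints include data after rescue.
- **Endpoint.** "Tier 1 endpoints for hypoglycemia are the percentages of participants experiencing 1 or more episodes of symptomatic hypoglycemia". The Tier 2 endpoints, documented and severe hypoglycemia, are also percentages of participants with at least one episode.
- **Population and strata.** Section 9.5.2: "Safety analyses will be performed in the APaT population consisting of all randomized participants who received at least one dose of study treatment". Participants with and without background insulin are analysed apart: "Analyses of hypoglycemia combining participants on and not on a background of insulin are not planned".
- **Comparison.** Tier 1 events get p-values and 95% CIs for "between-treatment differences in the proportion of participants with events; these analyses will be performed using the M&N method". Tier 2 events get the CI by the same method. Neither has an exposure term.

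The double-blind period is about 54 weeks, "including a 24-week Phase A + 30-week Phase B" (Section 4.1). From Week 24 the intensification trigger is FFSG >130 mg/dL together with FS A1C >7.5% (Section 6.5.1, Table 4). No incidence rate, time-to-first-episode analysis or including-rescue analysis of hypoglycemia is specified.

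**The concern.** A percentage with at least one episode is comparable between arms only if the arms are watched for similar lengths of time. Here a participant who is intensified at Week 24 stays in the denominator for Phase A+B, but the remaining 30 of 54 weeks cannot contribute an episode. The event that stops counting is poor glycemic control, which the drug is meant to reduce. The arm with better control is therefore expected to be watched for longer and to record more first episodes, even if the weekly risk is identical.

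This affects a Tier 1 endpoint that is tested with a p-value, in a trial with safety over 24 and 54 weeks as a primary objective. It also understates the 54-week risk in both arms. Leaving out post-rescue episodes is a separate choice and is not disputed here: the rescue is insulin, which itself causes hypoglycemia.

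**Working it through.** **1. The plan's own figure.** Section 9.6.2 sets the Tier 2 thresholds at 8 ertugliflozin or 2 placebo participants, because with fewer the 95% CI always includes zero. At zero difference the Miettinen-Nurminen statistic is z = d / √[p(1−p)(1/n₁+1/n₂)·N/(N−1)]. With n = 110 and 55:

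- 7/110 vs 0/55 gives p = 0.057, and 8/110 vs 0/55 gives p = 0.041.
- 0/110 vs 1/55 gives p = 0.157, and 0/110 vs 2/55 gives p = 0.045.

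Both thresholds reproduce from participant counts alone. Observation time does not enter.

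**2. Inputs.** From the documents: A1C difference −0.6% (treatment policy) or −0.75% (treatment effect), SD 1.5% (Section 9.9); trigger A1C >7.5%; 24 + 30 weeks. Not given, so assumed: placebo Week 24 A1C mean m = 7.5–8.5%; the share f = 0.5–1.0 of those above 7.5% who also have FFSG >130 mg/dL; and an equal, constant hypoglycemia hazard giving a 20% risk over 54 weeks.

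**3. Simplest case: counting stops only at Week 24** (m = 8.0, difference 0.6, f = 1).

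- Placebo stopping: P(Z > (7.5−8.0)/1.5) = 63%. Ertugliflozin (mean 7.4): P(Z > (7.5−7.4)/1.5) = 47%.
- Weeks at risk: 54 − 30×0.631 = 35.1 against 54 − 30×0.473 = 39.8, a ratio of 1.13. With f = 0.75 it is 1.09, and with f = 0.5 it is 1.05.
- Risk by Week 24: 1 − 0.8^(24/54) = 9.4%. Crude percentages: placebo 0.631×9.4 + 0.369×20 = 13.3%; ertugliflozin 0.473×9.4 + 0.527×20 = 15.0%. The ratio is 1.12, an excess of 1.7 points with no true difference.

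Over m = 7.5–8.5, SD 1.2 or 1.5, difference 0.6 or 0.75 and f = 0.5–1.0, the crude ratio runs from 1.04 to 1.21.

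**4. Adding Phase A rescue and Week 38 intensification.** Assumed rescue is 15% placebo and 7% ertugliflozin. Pooled 2:1 this is (15 + 2×7)/3 = 9.7%; with 3.9% stopping study medication the total is 13.6%, inside the 14% of Section 9.9. With rescue given to the highest A1C values, the crude ratio is 1.10–1.15 (1.5–1.9 points at a 20% risk). If the hazard also falls as A1C rises, it is 1.04–1.14 (0.8–1.8 points).

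**5. Upper end.** Assumed rescue of 20% vs 8%, unrelated to A1C, with a high intensification share, can give 20.6% vs 17.4% where full observation would give 26.8% in both arms: ratio 1.18, 3.2 points.

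**6. Phase A alone.** A rescue spread evenly over Weeks 6–24 loses 9 weeks on average. Weeks ratio: (24 − 9×0.07)/(24 − 9×0.15) = 23.37/22.65 = 1.03. With rescue of 20% vs 10% it is 1.04.

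**7. Effect on the test.** With no true difference and a placebo percentage of 10–30%, two-sided rejection at n = 110/55 is 5.1–6.0% when the crude ratio is 1.09 and 5.9–10.7% when it is 1.19. In assumed half-size insulin strata it is 4.6–5.5% and 4.9–7.7%.

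**8. A person-time rate under the same conditions.** Where the hazard is unrelated to who stops, the first-episode rate ratio is 1.00. With an assumed log-hazard slope of −0.5 per 1% A1C and rescue on the highest A1C values, the crude ratio is about 1.06–1.10 and the rate ratio is 0.93–0.97.

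**The case against.** Much of the case on the other side stands.

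- **The size is not in the documents.** No rate of intensification or hypoglycemia by arm is stated. A reader might infer a definite excess near 20%, or take the relative figure as percentage points. Neither is supported. The top of the range needs high, unequal stopping, for example rescue unrelated to A1C, although rescue is triggered by high FPG. Rescue of 20% vs 8% pools to (20 + 2×8)/3 = 12%; adding 3.9% discontinuation gives about 16%, above the plan's 14%.
- **Those who stop are probably at lower risk.** They have high A1C and high fasting glucose. This moves the bias to the lower end but does not remove it.
- **A rate is not a clean replacement.** In step 8 it errs the other way, by a slightly smaller amount, and would understate hypoglycemia on ertugliflozin. A reader might conclude that the Tier 1 p-value should move to the rate; that does not follow, because an error that hides harm is no improvement in a pediatric safety analysis.
- **The test is only modestly affected**, most clearly within insulin strata (step 7).
- **Part of the answer is already planned.** The same endpoints are analysed for Phase A alone, and Table 6 lists the proportions rescued or intensified.

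The last point does not close the gap. Those proportions are exploratory and are not tied to the hypoglycemia comparison. The days on therapy in Section 9.12 do not measure time to rescue, since rescued participants continue study drug (Section 8.10.5). The caution in Section 9.6.2 that unadjusted CIs are descriptive does not withdraw the Tier 1 p-value.

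**Conclusion.** The point holds in a limited form. For Phase A+B, the crude percentages compare arms with unequal expected time at risk, and nothing planned shows or adjusts for this. The direction, against ertugliflozin, follows from the planned A1C effect and the Phase B trigger; it is an expectation, not something the documents state. The size rests on assumed rescue, intensification and hypoglycemia rates: about 5–20% relative, roughly 1–3 percentage points at a 54-week risk of 20–27%, and towards the lower end if those who stop are at lower hypoglycemia risk. Phase A alone is little affected. This does not invalidate the safety analysis, but a small Phase A+B difference could not be read as a drug effect without knowing the time at risk.

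**What to change.** In Section 9.6.2, for the Phase A+B excluding-rescue Tier 1 and Tier 2 hypoglycemia endpoints, add within each background-insulin stratum:

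- the exposure-adjusted first-episode rate, with time running from first dose to the earliest of first episode, rescue or intensification, or last dose + 14 days;
- the between-group rate difference or ratio with its 95% CI;
- mean time at risk per arm, shown beside the crude percentage.

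Keep the Miettinen-Nurminen p-value as planned. State that any crude Phase A+B difference will be interpreted together with the rate and the Phase A result, and that the rate may understate hypoglycemia on ertugliflozin because censoring at rescue may be informative.

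The cost is a short addition to the SAP and one extra table, with no new data collection. It should be written in before unblinding.
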